### 3.5.3 Administration of Study Drug

Acalabrutinib capsule is to be taken orally approximately every 12 hours.

The capsules should be swallowed intact with water. Subjects should not attempt to open capsules or dissolve them in water. Acalabrutinib can be taken with or without food.

If a dose is missed, it can be taken up to 3 hours after the scheduled time with a return to the normal schedule with the next dose. If it has been > 3 hours, the dose should not be taken and the subject should take the next dose at the scheduled time. The missed dose will not be made up and must be returned to the site at the next scheduled visit.

Guidance on co-administration of acalabrutinib with agents that affect gastric pH is provided in [Section 3.10.2](#).

R-ICE will be administered as per standard institutional policy.

### 3.5.4 Assuring Subject Compliance

For treatments that are taken in the clinic, subjects should take the dose from the drug dispensed for them for that particular time period. All other acalabrutinib treatments will be taken at home. Subjects will receive a medication diary to record the specific time each dose was taken and to record reasons for any missed doses (Appendix 6).

Subject compliance with acalabrutinib dosing will be assessed at every clinic visit. The subject will be instructed to bring the diary and any remaining capsules to the clinic at their next visit. The study staff will review the diary and ask the subject if all of the capsules were administered. Any remaining or returned capsules will be counted and recorded as described in [Section 7.6](#). Returned capsules must not be redispensed to another subject.

## 3.6 STUDY TREATMENT SCHEDULE

This is a phase II study of acalabrutinib in combination with R-ICE for rel/ref DLBCL non-GC-subtype. R-ICE will be administered as per standard institutional policy.

## 3.7 DURATION OF THERAPY

In the absence of treatment delays due to adverse event(s), treatment may continue for 3 cycles or until one of the following criteria applies:

- Disease progression,
- Intercurrent illness that prevents further administration of treatment,
- Unacceptable adverse event(s),
- Patient decides to withdraw from the study, or

- General or specific changes in the patient's condition render the patient unacceptable for further treatment in the judgment of the investigator.

Patients that achieve a partial or complete remission following 3 cycles of therapy, per criteria outlined in Section 4.1.16, and have mobilized  $\geq 2 \times 10^6$  CD34+/kg, will be eligible to proceed to autologous transplantation at the discretion of the treating physician. Patients will have completed study following 3 cycles of therapy and will be subject to follow-up per Section 4.2 and 4.3.

### 3.8 DOSING DELAYS AND MODIFICATIONS

#### Treatment modifications

Treatment-emergent adverse events of R-ICE therapy predominantly comprise of hemato-toxicities (such as neutropenia, leukopenia, thrombocytopenia, and anemia). Nonhematologic disorders include asthenia, sensory disturbance, mucositis, alopecia, sepsis, dyspnea, back pain, hyperglycemia, hypersensitivity, and cardiac disorders. Tumor lysis syndrome will be managed as per institutional guidelines. Renal and hepatic adverse reactions will be managed as per institutional guidelines. Treatment modifications are not permitted for R-ICE.

#### Cycle delay

After completion of each 21-day cycle, the start of a new cycle could be delayed for up to one 1 week (7 days) in cases of toxicity necessitating a dose delay. A subject whose cycle is delayed should be assessed within a week for resolution or recovery of toxicity and a decision regarding further delay.

There is no limit on the number of cycle delays that each subject may experience, as long as delays do not exceed one week or 28 days from the beginning of a cycle.

The following parameters must be met on the first day of a new cycle (after cycle 1):

- Platelet count  $\geq 50 \times 10^9/L$
- ANC  $\geq 1.0 \times 10^9/L$
- Non-hematologic toxicity of  $\geq$  grade 3 must have recovered to baseline or Grade  $\leq 1$

For severe hematologic toxicity (grade  $\geq 3$ ), laboratory evaluations may be repeated more frequently as necessary until the retreatment requirements are met. In the event of severe renal toxicity or hepatotoxicity, laboratory tests may be repeated more frequently as necessary until the toxicity resolves.

#### Dose modifications and dose limiting toxicities (DLT) acalabrutinib + RICE

Given that acalabrutinib has not been studied in phase I combination with R-ICE, a 3-6 patient lead-in will be conducted at the acalabrutinib 100 mg PO BID dosing. If one DLTs is observed within the first 3 patients, or if two DLTs are observed within the first 6 patients, a dose level (-)1 of acalabrutinib at 100 mg PO daily will be instituted for the next 3-6 patients. If  $> 2$  DLTs are observed within the next 6 patients, the study will be terminated.

#### Dose Limiting Toxicity: acalabrutinib + R-ICE

The DLT evaluation period begins with the first dose of acalabrutinib and ends immediately prior to the initiation of the second cycle. Only toxicities that occur during the DLT period will be used for the purposes of defining DLT. However, toxicities that occur in all cycles will be considered in the overall decisions of the investigators. The first 3-6 subjects will be evaluated for DLTs per above. Subjects considered non-evaluable for DLT may be replaced, but the safety profile of these subjects will be included in the investigator review. Subjects considered non-evaluable for DLT are subjects who do not complete Cycle 1 for reasons other than toxicity. Subjects who experience a DLT may continue treatment on the study at a lower dose of acalabrutinib.

The following will be considered DLTs after confirmation by the investigators:

- Complete treatment interruption of more than 7 days (28 days of the cycle) for acalabrutinib-RICE-related Grade  $\geq 2$  toxicities within Cycle 1

- Any Grade 3 or Grade 4 non-hematological toxicity that is at least possibly related to the study drugs
  - excluding:
    - Grade 3 nausea or vomiting responsive to anti-emetic treatment,
    - Grade 3 diarrhea responding to anti-diarrheal treatment,
    - Grade 3 fatigue/asthenia unless persisting for 7 days after stopping acalabrutinib and absent at baseline
    - alopecia
  - including:
    - persistent Grade  $\geq$  2 nausea and/or vomiting despite prolonged (more than 7 days continuously) anti-emetic treatment (5 HT3 antagonist, antihistamine, metoclopramide)
- Grade  $\geq$  2 hemorrhagic events requiring medical intervention
- Grade 4 hematological toxicity defined as:
  - Febrile neutropenia (ANC < 500 cells/ $\mu$ L with fever [body temperature  $\geq$  38.5°C] or sepsis) or Grade 4 neutropenia (ANC < 500 cells/ $\mu$ L) requiring at least 1 week delay of the next treatment cycle
  - Grade 4 thrombocytopenia (Platelet count < 25,000 cells/ $\mu$ L) requiring at least 1 week delay of next treatment cycle

Based on the specific adverse event observed, 1 dose level reduction is permitted for acalabrutinib (see Table below). If acalabrutinib is withheld for  $\leq$  1 week due to acalabrutinib-related toxicity; study drug should be resumed with a dose reduction when treatment resumes following recovery from the toxicity. If there is unacceptable toxicity despite 1 dose reduction the treatment should be discontinued. If treatment must be withheld for an acalabrutinib-related adverse event that fails to resolve to an acceptable level (eg,  $\leq$  Grade 1 nonhematologic toxicity) within 1 week after the date acalabrutinib was withheld, treatment with acalabrutinib should be permanently discontinued. In this event, the subject will be discontinued from the treatment, and End-of-Treatment Visit assessments will be performed including through the protocol-specified AE reporting window and have follow-up for ongoing SAEs to resolution or stability unless the subject lost to follow-up. (see section 6.2.6)

Acalabrutinib dose adjustments also apply to cycle 1.

**Acalabrutinib** dose will not be reduced for hematological toxicities unless the hematologic toxicities fail to recover by day 21 of a cycle.

The actions in the table below should be taken for the following toxicities at day 21 of the cycle:

- Grade 4 ANC (<500/ $\mu$ L) for  $>7$  days
- Grade 3 thrombocytopenia (<50,000/mcL) in the presence of clinically significant bleeding events
- Grade 4 thrombocytopenia (<25,000/mcL)
- Grade 3 or 4 nausea, vomiting, or diarrhea, if persistent, despite optimal antiemetic and/or anti-diarrheal therapy
- Any other Grade 4 or unmanageable Grade 3 toxicity.

For Grade 3 or 4 atrial fibrillation or persistent atrial fibrillation of any grade, consider the risks and benefits of acalabrutinib treatment. *If clinically indicated, the use of anticoagulants or antiplatelet agents may be considered for the thromboprophylaxis of atrial fibrillation.*

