### **3.9.2.1 CYP Inhibiting/Inducing Drugs**

Based on available nonclinical and clinical data, acalabrutinib is almost completely metabolized by multiple CYP and non CYP metabolic pathways. CYP3A-mediated oxidation is the major route of metabolism in humans. Additional studies were performed in a human liver microsomal system with specific chemical inhibitors of individual CYP isoforms. Inhibition of acalabrutinib metabolism by specific CYP3A4/5 inhibitors (ketoconazole and troleandomycin) indicate that CYP3A4/5 is the predominant CYP isoform responsible for metabolism of acalabrutinib.

PBPK modeling predicted the magnitude of changes in acalabrutinib and active metabolite exposure due to a variety of moderate CYP3A inducers and inhibitors. Avoid coadministration of strong CYP3A inhibitors (such as itraconazole and rifampin) with acalabrutinib on study, if possible. If moderate or strong CYP3A inhibitors are required on study, monitor subjects for toxicity (refer to IB section 6.7). A list of common CYP3A4/5 inhibitors or inducers is provided at <http://medicine.iupui.edu/clinpharm/ddis/table.aspx>.

- If acalabrutinib must be administered with a strong or moderate CYP3A4/5 inhibitor, the Medical Monitor should be consulted before use, and a dose reduction of acalabrutinib to 100 mg PO daily or temporarily holding acalabrutinib should be considered. Patients should be closely monitored for potential treatment-related toxicities.
- There was minimal involvement of CYP1A2, CYP2E1, CYP2B6, CYP2C8, CYP2C9, CYP2C19, or CYP2D6 in the metabolism of acalabrutinib in human liver microsomes.. Therefore drugs that are known to be CYP1A2, CYP2E1, CYP2B6, CYP2C8, CYP2C9, CYP2C19, or CYP2D6 inhibitors or inducers are not restricted.

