### **3.9.2.5 Surgery**

Patients who require surgery for any reason while on study are recommended to withhold acalabrutinib for 3-7 days pre- and post-surgery, depending upon the type or surgery and the

risk of bleeding. Patients must have recovered adequately from any toxicity and/or complications from the intervention before the first dose or before restarting acalabrutinib.

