### **5.2.3 Study Treatment Administration and Compliance**

Descriptive information will be provided regarding the number of acalabrutinib doses prescribed, the total number of doses taken, the number of days of treatment, and the number and timing of prescribed dose delay, reductions and interruptions.

For each subject, acalabrutinib compliance will be described in terms of the proportion of study drug actually taken.

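### DLT evaluability in the lead-in depends on completing Cycle 1, with no minimum acalabrutinib exposure, so a patient who took far less than planned can count as DLT-free at 100 mg BID

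*Combined protocol and SAP*

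**What the plan says.** Under Section 3.8, because the combination has had no phase I study, "a 3-6 patient lead-in will be conducted at the acalabrutinib 100 mg PO BID dosing". One DLT in the first three patients, or two in the first six, leads to the lower dose level.

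The observation window is set by time: "The DLT evaluation period begins with the first dose of acalabrutinib and ends immediately prior to the initiation of the second cycle". The only exclusion from the count is "Subjects considered non-evaluable for DLT are subjects who do not complete Cycle 1 for reasons other than toxicity", and replacement is optional: "Subjects considered non-evaluable for DLT may be replaced".

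Other sections allow acalabrutinib to be interrupted without toxicity while the cycle continues. Under Section 3.9.2.5, patients needing surgery are "recommended to withhold acalabrutinib for 3-7 days pre- and post-surgery". Section 3.5.3 says of a dose more than 3 hours late: "The missed dose will not be made up and must be returned to the site at the next scheduled visit". It sets no limit on how many may be missed.

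Sections 3.4.2 and 3.11 provide for withdrawal of significantly noncompliant patients. Section 5.2.3 adds that "acalabrutinib compliance will be described in terms of the proportion of study drug actually taken".

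**The concern.** A DLT-free patient is evidence about a dose only if the patient took roughly that dose. Section 3.8 asks whether the cycle was completed, not how much acalabrutinib was taken. A patient with a long non-toxicity gap has had less opportunity for a DLT caused by the combination, yet enters the denominator at full weight.

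That denominator is 3 to 6, so one such patient is a third to a sixth of the evidence. The lead-in is the only numeric DLT rule for this combination. Its result sets the dose for the remaining 40 to 43 of 46 patients (46 − 6 and 46 − 3), if the lead-in patients belong to the 46 and both stages are completed. The error runs in one direction, towards clearing the starting dose.

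**Working it through.** The plan gives no clearing probability, error rate or minimum exposure for the lead-in, so there is no stated figure to reproduce.

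**Exposure in a completed Cycle 1.** Acalabrutinib is planned for days 1 to 21 (Synopsis, Study Design) about every 12 hours (Section 3.5.3), so 21 × 2 = 42 doses.

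- Shortest surgery hold: 3 + 3 = 6 days. Doses left: 42 − 12 = 30, and 30/42 = 71%.
- Longest surgery hold: 7 + 7 = 14 days. Doses left: 42 − 28 = 14, and 14/42 = 33%.
- Both figures require both holds to fall within Cycle 1.
- Missed doses: no limit is stated, so no lower bound can be calculated.

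Neither route by itself ends Cycle 1, so these patients are evaluable unless a site reads completion as completion of planned dosing.

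**Effect on the count.** Let p be the DLT probability at full exposure and f the relative risk of an under-exposed patient. Neither is in the documents. I take p = 0.20, 0.30 and 0.40, with f = 0.5 and, as an upper bound on the effect, f = 0. One of the first three patients is under-exposed. Because a single DLT in the first three triggers de-escalation, both paths below start with none in three.

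- Three-patient path: all fully exposed, (1 − p)³; one under-exposed, (1 − p)² × (1 − fp).
- Six-patient path: multiply by the probability of at most one DLT in the next three, (1 − p)³ + 3p(1 − p)².

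At p = 0.30:

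- 0.7³ = 0.343.
- With f = 0.5: 0.7² × 0.85 = 0.417 (rounded from 0.4165).
- With f = 0: 0.7² = 0.490.
- Multiplier: 0.343 + 3 × 0.30 × 0.49 = 0.784.
- Six-patient path: 0.343 × 0.784 = 0.269; 0.4165 × 0.784 = 0.327; 0.490 × 0.784 = 0.384.

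| Assumed p | Path | All fully exposed | One at half risk | One at zero risk |
|---|---|---|---|---|
| 0.20 | 3 patients | 0.512 | 0.576 | 0.640 |
| 0.20 | 6 patients | 0.459 | 0.516 | 0.573 |
| 0.30 | 3 patients | 0.343 | 0.417 | 0.490 |
| 0.30 | 6 patients | 0.269 | 0.327 | 0.384 |
| 0.40 | 3 patients | 0.216 | 0.288 | 0.360 |
| 0.40 | 6 patients | 0.140 | 0.187 | 0.233 |

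**Unconditional size.** The table supposes that one of the first three is under-exposed. If instead each patient has an assumed 10% chance of it, at half risk and p = 0.30, the chance that a patient is DLT-free is 0.9 × 0.70 + 0.1 × 0.85 = 0.715. The chance of none in three is then 0.715³ = 0.366, against 0.343.

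**The case against.** **Interacting drugs.** A reader might infer that the CYP3A inhibitor provision in Section 3.9.2.1, under which "a dose reduction of acalabrutinib to 100 mg PO daily or temporarily holding acalabrutinib should be considered", is another route to under-exposure, and that a patient reduced to 100 mg daily has in effect been observed at the lower dose level. The documents do not support this. Section 3.10.2 reports that itraconazole raised acalabrutinib exposure about 5-fold. Taken at face value, half the daily dose with that inhibitor gives 5 × 0.5 = 2.5 times the uninhibited daily exposure. Exclusion criterion 27 also removes patients who need a strong inhibitor at baseline and cannot switch. Such a patient is not a clean test of 100 mg BID, but under-exposure is not shown.

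**Noncompliance.** Section 3.5.4 checks diaries and capsules at every visit, and a patient withdrawn in Cycle 1 for noncompliance is already non-evaluable. This covers part of the missed-dose route. It has no threshold and no link to DLT evaluability, and it cannot cover a hold that the protocol itself recommends.

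**Meaning of completion.** The term could be read as completing planned dosing. That reading is possible, but nothing in the text requires it, and sites may differ.

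**Size.** Zero risk is too strong an assumption, because an under-exposed patient still receives R-ICE and the DLT list includes febrile neutropenia and cytopenias that delay the next cycle. The half-risk column is more reasonable, though also assumed. Surgery in Cycle 1 may be rare; the documents give no frequency.

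**Other oversight.** Section 3.8 has investigators consider toxicities from all cycles, and the monitoring committee (Section 3.13) can suspend the study. Both soften the consequence, but neither corrects the count on which the dose is cleared.

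**Conclusion.** The gap is real and modest. Evaluability rests on an undefined completion of Cycle 1, and no section sets a minimum exposure. Surgery holds and missed doses carry the point.

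If one of the first three patients is under-exposed, and the DLT rate is an assumed 30%, the chance of no DLT in three rises from 0.343 to 0.417 at half risk (upper bound 0.490). The six-patient path rises from 0.269 to 0.327 (upper bound 0.384). These figures are conditional on that event, whose probability is unknown, and rest on an assumed DLT rate and relative risk. The gap in the wording does not depend on them.

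A reader might go further and infer that the lead-in is likely to clear an unsafe dose. The documents give neither the DLT rate nor the frequency of under-exposure, so they cannot support that. This is a cheap improvement to the design, best made before the lead-in is assessed.

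**What to change.** In Section 3.8, define a DLT-evaluable lead-in patient as one who either has a DLT, or completes the DLT period having taken at least a prespecified share of planned Cycle 1 acalabrutinib together with the Cycle 1 R-ICE. An 80% share, for example, is at least 34 of 42 doses (0.80 × 42 = 33.6). The documents give no such figure, so the sponsor should set it. Then state that:

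- a shortfall caused by toxicity leaves the patient evaluable, so that toxicity is never excluded;
- a patient short for any other reason is replaced for the DLT count only, and stays in the CR and safety analyses, which fits the no-replacement rule for treated patients in Section 3.4.4;
- patients whose dose was changed for an interacting drug are counted by a rule fixed in advance, since a capsule count does not measure their exposure.

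The cost is protocol wording. Diaries and capsule counts are already collected (Sections 3.5.4 and 7.5). One or more further patients may need observation in the DLT window, with a slightly longer lead-in. They would come from the 20 planned for stage 1, if lead-in patients are part of that stage, which should be stated. No dose, hold or stopping rule changes.

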### **Non-hematological grade 3 or higher toxicities**

- For Grade 3 possible or probable acalabrutinib-related non-hematologic toxicities (other than the adverse events specifically described in this section), therapy (acalabrutinib and R-ICE) is to be held for a maximum of 1 week (and d28 of a cycle) until the toxicity returns to Grade 1 or less. If grade 2 during the first cycle, this will be considered a DLT.
- For any Grade 4 non-hematologic toxicity attributed to acalabrutinib, discontinue acalabrutinib and chemotherapy for all remaining cycles; subject is discontinued from study treatment and must complete protocol-specified AE reporting along with follow-up for ongoing SAEs to resolution unless the subject is lost to follow-up.
- If Grade 3 toxicity returns to Grade 1 or less by Day 28, then proceed with next cycle of therapy with acalabrutinib reduced to the next lower dose level.

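### Section 3.8 both stops and dose-reduces acalabrutinib for a Grade 4 non-hematologic event attributed to it, because the day-21 list has no exception for the stop rule

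*Combined protocol and SAP*

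**What the plan says.** All of the relevant text is in Section 3.8.

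- **Stop rule**, under *Non-hematological grade 3 or higher toxicities*: "For any Grade 4 non-hematologic toxicity attributed to acalabrutinib, discontinue acalabrutinib and chemotherapy for all remaining cycles".
- **Day-21 list**, under *Dose Limiting Toxicity: acalabrutinib + R-ICE*: "The actions in the table below should be taken for the following toxicities at day 21 of the cycle". Its entries include "Grade 3 or 4 nausea, vomiting, or diarrhea, if persistent, despite optimal antiemetic and/or anti-diarrheal therapy" and "Any other Grade 4 or unmanageable Grade 3 toxicity". The table is the *Dose Reduction Schedule for Acalabrutinib*. It has one step, from 200 to 100 mg/day, and bars anything lower.
- **Resume sentence**, same subsection as the list: after acalabrutinib has been withheld for up to one week for toxicity related to it, "study drug should be resumed with a dose reduction when treatment resumes following recovery from the toxicity".
- **Atrial fibrillation sentence**, same subsection: "For Grade 3 or 4 atrial fibrillation or persistent atrial fibrillation of any grade, consider the risks and benefits of acalabrutinib treatment".
- **DLT sentences**, same subsection: the DLT definition includes "Any Grade 3 or Grade 4 non-hematological toxicity that is at least possibly related to the study drugs", with some exclusions, and "Subjects who experience a DLT may continue treatment on the study at a lower dose of acalabrutinib".

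Nothing in Section 3.8 says which of these prevails when two of them apply.

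**The concern.** The stop rule and the day-21 list are both mandatory. The stop rule covers every Grade 4 non-hematologic event attributed to acalabrutinib. The list names Grade 4 gastrointestinal events and then sweeps in all other Grade 4 toxicity, and it says nothing about attribution. An attributed Grade 4 event present at day 21 therefore falls under both.

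An investigator who follows the list gives the patient more acalabrutinib, at half the dose, after a Grade 4 event judged to be caused by it. One who follows the stop rule ends acalabrutinib and the salvage chemotherapy. The three centers could handle the same event in opposite ways without any of them deviating from the protocol. Section 3.8 itself notes that this combination has no phase I data, so the toxicity rules are a main safeguard.

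**Working it through.** The plan states no figure on this point, so the check is a comparison of rules, followed by a rough size.

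**1. The two mandatory rules**

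- Stop rule. Event: Grade 4, non-hematologic, attributed to acalabrutinib. Timing: any. Action: end acalabrutinib and chemotherapy.
- Day-21 list. Event: persistent Grade 4 nausea, vomiting or diarrhea despite optimal therapy, or any other Grade 4 toxicity. Timing: day 21 of the cycle. Attribution: not mentioned. Action: the table, that is, 200 to 100 mg/day.

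The overlap is an attributed Grade 4 non-hematologic event present at day 21. The actions are incompatible there, since a patient cannot both stop and continue at 100 mg/day.

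**2. What narrows the overlap**

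Section 3.8 also says that acalabrutinib is permanently discontinued if a related event for which it was withheld does not settle within 1 week. If that rule is given effect, an attributed event that led to a hold before about day 14 (21 − 7) and is still present at day 21 has already ended treatment. The list then matters mainly for holds that began in the last week of the cycle, or where drug was not held.

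**3. Does the Grade 3 exception help?**

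The subsection with the stop rule exempts adverse events dealt with elsewhere in the section, but the exemption is attached to its Grade 3 bullet. The Grade 4 bullet has none. The exemption therefore does not make the day-21 list prevail at Grade 4.

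**4. The three softer sentences**

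- Resume sentence: it sets the dose once a withheld drug is restarted. The stop rule's subsection holds treatment at Grade 3 and discontinues at Grade 4, so an event that is discontinued need never reach the resume sentence.
- Atrial fibrillation sentence: it asks for a judgement, and stopping satisfies it.
- DLT sentence: it is permissive, and stopping satisfies it.

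None of the three clearly contradicts the stop rule, but none refers to it.

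**5. Size**

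The documents give no rate of attributed Grade 4 non-hematologic toxicity. Let g be an assumed per-patient rate and f the assumed share of such events present at day 21. The chance of at least one patient in the overlap is 1 − (1 − g·f)^n, with n = 46 for the full trial or 20 if it stops after stage 1 (Section 5.1). The expected number with f = 1 is 46g.

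| g | 46g | n=46, f=1 | n=46, f=0.5 | n=46, f=0.25 | n=20, f=1 |
|---|---|---|---|---|---|
| 1% | 0.46 | 0.37 | 0.21 | 0.11 | 0.18 |
| 2% | 0.92 | 0.61 | 0.37 | 0.21 | 0.33 |
| 5% | 2.3 | 0.91 | 0.69 | 0.44 | 0.64 |
| 10% | 4.6 | 0.99 | 0.91 | 0.69 | 0.88 |

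Example: g = 2%, f = 0.5, n = 46 gives 1 − 0.99^46 = 0.37. The f = 1 columns count every attributed Grade 4 event and are ceilings for the conflict. Every entry depends on assumed g and f.

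**The case against.** The strongest reply is that Section 3.8 can be read as one scheme. The stop rule stands under a heading for Grade 3 or higher non-hematologic toxicity and supplies the grade split. The day-21 list would then cover hematologic events and events not attributed to acalabrutinib. Investigators may also stop treatment at any time in the patient's interest (Sections 3.7 and 3.11), and the DSMC reviews adverse events with Section 3.8 before it (Section 3.13).

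Part of this stands. It disposes of several stronger conclusions that a reader might draw:

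- That the resume sentence orders re-exposure after an attributed Grade 4 event. It is conditional on drug having been withheld, and it does not say which events may be held rather than stopped.
- That the atrial fibrillation and DLT sentences keep such patients on treatment. Both leave room to stop.
- That the ambiguity costs power. Any loss of complete responses among stopped patients would come from applying the stop rule, which the plan already contains. Appendix 1, footnote i, also lets scans after fewer than 3 cycles serve as the end-of-treatment assessment. A power figure would not measure this conflict.
- That patients who start at 100 mg daily after a lead-in de-escalation could be given a forbidden dose. The 100 mg/day floor already prevents it.

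The reply does not dispose of the day-21 list. The list names Grade 4 vomiting and diarrhea, adds all other Grade 4 toxicity, and has no attribution limit. Confining it to events not attributed to acalabrutinib means supplying words that the text lacks. The freedom to stop protects a cautious investigator's patient, but it does not make continuing under the list a deviation.

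**Conclusion.** The point holds for one pair of instructions. For a Grade 4 non-hematologic event attributed to acalabrutinib and present at day 21, Section 3.8 requires both discontinuation of all protocol treatment and an acalabrutinib dose reduction. The resume, atrial fibrillation and DLT sentences are loose ends rather than contradictions.

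The consequence is one of patient safety and consistency between centers, not of the primary analysis. The likely number of patients is small but cannot be fixed from the documents. This should be corrected because the wrong branch re-exposes a patient after a Grade 4 event blamed on the drug. Confidence in the textual conflict is high. It rests on reading the table that the list points to as the dose-reduction schedule, the only table that follows it in Section 3.8.

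**What to change.** 1. In the day-21 list, add an exception: non-hematologic events of Grade 4 that are attributed to acalabrutinib are discontinued under the non-hematological toxicity rule.
2. Cross-refer to that rule in the resume, atrial fibrillation and DLT sentences.
3. If the sponsor prefers dose reduction or a risk-benefit judgement for particular Grade 4 events, such as vomiting, diarrhea or atrial fibrillation, name them as exceptions in the stop rule instead. Either way, each event then has one action.
4. Optional: add a row to the dose-reduction schedule for patients who start at 100 mg daily, stating that no reduction is available and what to do after a toxicity that has recovered.

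The cost is a few phrases and one sponsor decision, with no added patients or procedures. The clinical downside of letting the stop rule govern is that protocol chemotherapy also ends for the affected patients, which that rule already requires.
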